10 DISCONTINUATION AND REPLACEMENT OF SUBJECTS

10.1 Early Discontinuation of Study Treatment

The administration of lucinactant for inhalation may be discontinued at any time prior to the completion of dosing based on certain criteria (Section 6.8) or the clinical judgment of the PI. Subjects whose treatment is discontinued based on the PI's judgment will continue in the study. Subjects whose treatment is discontinued based on the parent/guardian's wishes must be withdrawn from the study.

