The administration of study treatment may be discontinued at any time prior to the completion of dosing if certain device malfunctions or interruptions occur which cannot be corrected in a safe and timely manner or based on the clinical judgment of the PI. Reasons for discontinuation of study treatment include, but are not limited to the following:

1. A device malfunction occurs
2. The device shuts down as a result of a detected out of range condition
3. An AE or ADE which places subject at risk occurs (eg, pulmonary hemorrhage; airway obstruction)
4. If, in the PI's best medical judgment, initiating or continuing the subject's exposure to study treatment is not in the best interest of the subject's safety
5. Signs of acute respiratory deterioration develop, as evidenced by a clinically significant increase in respiratory rate or effort (work of breathing) plus at least one of the following:
 - a) A persistent (at least 10 minutes) $\text{FiO}_2 \geq 0.70$ or sustained increase from baseline by ≥ 0.30 to maintain SpO_2 90% to 95%
 - b) A persistent (at least 5 minutes) transcutaneous $\text{PCO}_2 > 70 \text{ mmHg}$ or an increase from baseline by $\geq 20 \text{ mmHg}$
 - c) Recurring episodes of bradycardia
 - d) A sustained apneic event (≥ 20 seconds)

Subjects whose treatment is discontinued based on the PI's judgment will continue in the study. Subjects whose treatment is discontinued based on the parent/guardian's withdrawal of consent will be withdrawn from the study and no further data collection will be done.

Statistical Analysis The statistical analysis of objectives will be based on all enrolled preterm neonates. The subjects enrolled open-label with active treatment (the first 2 subjects from each site) will be summarized separately; however, AEs and other safety information may also be pooled with data from the double-blind portion of the study.

For the efficacy analysis, populations of all randomized subjects who received any treatment (modified intent-to-treat [mITT]) and subjects with no major protocol deviations or treatment interruptions (per-protocol) will be evaluated, based upon the treatment group to which they were randomized. For the safety analysis, all subjects randomized to the control group or who received any lucinactant for inhalation (including partial doses) will be evaluated, based upon the treatment they actually received.

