6.8 Early Discontinuation of Study Treatment

The administration of study treatment may be discontinued at any time prior to the completion of dosing if certain device error codes occur which cannot be corrected in a safe and timely manner or based on the clinical judgment of the PI. Reasons for discontinuation of study treatment include, but are not limited to the following:

1. Device failure or malfunction occurs. If device failure or malfunction occurs, the user should follow the on-screen instructions to resolve the issue. If they are unable to resolve the issue, they must contact the previously-identified Windtree representative for further instructions (Section 9.2).
2. Automatic treatment interruption due to a pre-defined condition (eg, syringe high pressure error). If automatic shutdown occurs, Windtree personnel should be contacted as soon as possible (per Section 9.2).
3. An AE or ADE which places subject safety at risk (eg, pulmonary hemorrhage, airway obstruction).
4. If, in the PI’s best medical judgment, continuing the subject’s exposure to study treatment is not in the best interest of the subject’s safety.

5. Signs of acute respiratory deterioration develop, as evidenced by a clinically significant increase in respiratory rate or effort (work of breathing) plus at least one of the following:
 - a. A persistent (at least 10 minutes) $\text{FiO}_2 \geq 0.70$ or a sustained increase from baseline by ≥ 0.30 to maintain SpO_2 90% to 95%
 - b. A persistent (at least 5 minutes) transcutaneous $\text{PCO}_2 > 70$ mm Hg or an increase from baseline by ≥ 20 mm Hg
 - c. Recurring episodes of bradycardia
 - d. A sustained apneic event (≥ 20 seconds)

Subjects whose treatment is discontinued based on the PI's judgment will continue in the study. Subjects whose treatment is discontinued based on the parent/guardian's withdrawal of consent must be withdrawn from the study and no further data collection will be done.

In accordance with local institutional practices, an approved SRT must be made available to subjects demonstrating a clinical need if dosing is discontinued early.

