10.2 Withdrawal of a Subject from the Study

A subject may withdraw consent (through their legally authorized representative) at any time without prejudice to further care.

If a subject is discharged or transferred to another hospital before 36 weeks PMA, the clinical status, including presence or absence of BPD at 36 weeks PMA, should be obtained. If, for any reason, the status of a subject is unknown (eg, subject is discharged home), every effort must be made to contact the subject's legally authorized representative to determine the status of the subject, including phone calls and certified letter(s). If the status of the subject has not been established in 28 days after the subject reaches 36 weeks PMA, the subject will be considered lost to follow-up. Note: All attempts should be made to ensure that no subjects are lost to follow-up.

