4.3 Missing Data

Missing values represent a potential source of bias in a clinical trial. Hence, every effort will be undertaken to fulfill all the requirements of the protocol concerning the collection and management of data; however, some missing data is inevitable. No imputation, including last observation carried forward, will be done for the any parameters; only available data will be considered.

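### Protocol 10.1 withdraws an infant from the study when a parent wants treatment stopped; 6.8 and the summary tie this to withdrawn consent; none provides for stopping treatment with follow-up continuing

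*Protocol*

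**What the plan says.** Three places in the protocol deal with treatment stopped at the parent's instance.

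- **Section 10.1.** Infants stopped on the investigator's "judgment will continue in the study". Infants stopped on the parent's or guardian's "wishes must be withdrawn from the study". The section does not mention data collection.
- **Section 6.8.** Infants whose treatment is stopped on the parent's or guardian's "withdrawal of consent must be withdrawn from the study and no further data collection will be done".
- **Section 1.1, Early Discontinuation of Treatment.** The same rule as 6.8: "withdrawal of consent will be withdrawn from the study and no further data collection will be done".

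Section 10.2 states the right to leave separately: "A subject may withdraw consent (through their legally authorized representative) at any time without prejudice to further care". It also asks sites to establish the status of infants discharged, transferred or otherwise of unknown status.

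The primary endpoint (Section 4.3.1) is respiratory failure due to RDS, or death, through day 28. On missing data, SAP 4.3 rules out imputation and says "only available data will be considered". Under Section 10.4, withdrawn infants are not replaced unless the DMC requires it.

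**The concern.** Stopping study treatment and refusing further use of data are different decisions. Section 10.1 makes the first a ground for leaving the study. Sections 6.8 and 1.1 speak only of withdrawn consent and do not address a parent who declines dosing but keeps consent. A site that receives such a request would withdraw the infant under 10.1 and find no instruction under 6.8.

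The outcome at stake can usually still be had. Intubation, surfactant and death are facts in the hospital record. The protocol already follows infants after an investigator's stop (10.1), after rescue surfactant (8.6.1) and after respiratory failure (4.3.1). The treatment policy strategy in Section 13.1 uses the primary variable whether or not treatment was interrupted, so it needs outcomes observed after a stop. The SAP intends the estimated difference for planning later studies and as supporting evidence of efficacy (SAP 4.2), so avoidable missing outcomes would carry forward.

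**Working it through.** **1. The rules side by side**

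| Place | Trigger | Stays in study? | Data collection |
|---|---|---|---|
| 10.1, 6.8, 1.1 | Investigator's judgment | Yes | Continues |
| 10.1 | Parent's wishes about treatment | No | Not mentioned |
| 6.8, 1.1 | Parent's withdrawal of consent | No | Ends |
| None | Parent stops dosing, allows follow-up | No rule, unless 10.1 applies | No rule, unless 10.1 applies |

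Section 10.1 does not itself end data collection. Section 4.3.1, however, follows infants with respiratory failure until they complete the study or withdraw, so withdrawal is treated there as the end of follow-up. It is on that reading that 10.1 loses later outcomes. Events before withdrawal still count.

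**2. How much follow-up comes after a stop**

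Randomization is within 6 hours of birth and repeat treatment is allowed up to 36 hours after it (Sections 6.4.1 and 6.6). Dosing therefore ends at about 6 + 36 = 42 hours of life at the latest. The endpoint window is 28 × 24 = 672 hours, and 42/672 = 6%. Most of the window, measured in time, follows any stop. This is a share of time, not of events.

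**3. Size at the planned enrolment**

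The documents give no number of parent-requested stops and no dropout allowance, so there is no plan figure to reproduce. Let w be the number of outcomes lost in one arm of n; w is assumed. The best/worst-case range of the difference has width w/n. With n = 65 (Protocol Section 3.2):

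- w = 1: 1/65 = 1.5 points
- w = 2: 3.1 points
- w = 3: 4.6 points
- w = 5: 7.7 points

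Some SAP tables show up to 35 per arm, which would give 1/35 = 2.9 points per infant.

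For illustration, take 44% versus 32% from the earlier study's infants without interruptions (Protocol 3.2.3.5), a difference of 12 points. Suppose the losses are in the active arm only and 32% is the rate among those observed. The active rate then lies between 0.32(65 − w)/65 and [0.32(65 − w) + w]/65.

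- w = 1: 31.5% to 33.0%; difference 11.0 to 12.5 points
- w = 5: 29.5% to 37.2%; difference 6.8 to 14.5 points

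**4. Direction**

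Under available-data analysis the denominator falls too. Take a control arm with 44% of 65 = 28.6 expected failures and one infant lost.

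- If that infant would have failed: (28.6 − 1)/64 = 43.1%, which is 0.9 points low.
- If not: 28.6/64 = 44.7%, which is 0.7 points high.

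**5. The 12 infants enrolled**

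The arm sizes are not given. The first two infants at each site receive open-label active treatment, and SAP 4.1 does not summarise them separately. Assume s enrolling sites with at least two infants each and an even split of the rest. The active arm then has 2s + (12 − 2s)/2 = 6 + s infants, and control has 6 − s.

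| s (assumed) | Active / control | One outcome in active | One outcome in control |
|---|---|---|---|
| 1 | 7 / 5 | 14.3 points | 20.0 points |
| 2 | 8 / 4 | 12.5 points | 25.0 points |
| 3 | 9 / 3 | 11.1 points | 33.3 points |

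**The case against.** The strongest reply is that this is loose wording. Section 10.1 may be shorthand for 6.8, and ending collection after true withdrawal of consent is proper. The consent form is a separate document (Section 12.2) that is not available here, and it may offer partial withdrawal. Section 10.2 also asks for every effort to trace infants of unknown status. Much of this stands. It does not remove the conflict, because 10.1 as written makes withdrawal mandatory on wishes about treatment, and the tracing duty, whose example is discharge home, does not lift that.

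A reader might infer that a parent's request to stop dosing ends data collection. No section says so: the end of collection appears only in 6.8 and the summary, under withdrawn consent.

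A reader might also infer that failure rates are biased downwards because parents ask to stop when the infant is doing badly. The documents give no evidence for this, and parts of the design weaken it. Study treatment is given only to infants stable enough not to need intubation (3.2.2). Deterioration and investigator judgment are separate stopping reasons (6.8), and an investigator's stop keeps the infant in the study. Parents of infants in the masked part do not know the assignment.

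Nor do the documents support saying that the analysis of all randomised infants is broken. The protocol's efficacy population is the treated, modified intent-to-treat set. The trial is described as an estimation study, and the SAP does no testing and does not evaluate intercurrent events.

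**Conclusion.** The concern holds as a conflict between sections with an avoidable loss of outcomes. Section 10.1 sets a different trigger from 6.8 and the summary, and no section provides for a treatment-only stop with follow-up. The avoidable loss is confined to infants whose parents want only treatment stopped and who have not yet reached the endpoint.

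At 65 per arm the cost is about 1.5 points of best/worst-case range per lost outcome in one arm. This rests on an assumed count, since none is given, and on reading withdrawal under 10.1 as the end of follow-up. The direction of bias is open.

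For the terminated study the effect may be nil. The documents report no such withdrawal, and only 12 infants were enrolled. The point matters mainly for any later protocol that reuses this wording.

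**What to change.** Reconcile Sections 10.1, 6.8 and 1.1 on one distinction:

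- A parent's request to stop study treatment alone leaves the infant in follow-up to day 28 and 36 weeks PMA.
- Data collection ends only when consent to data collection is withdrawn.

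On any such request, record which of the two the parent chose, and whether hospital-record data on intubation, surfactant and survival may still be used. The SAP's list of reasons for stopping treatment early (SAP 3.1) has no parent-request category; add one. For the 12 infants, state in the disposition summary whether any parent-requested stop occurred and, where permitted, the day-28 status.

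This changes follow-up and data handling only, not when treatment is stopped. The cost is protocol and consent-form wording and one recorded item. No sample size changes, because none was derived from a dropout rate. A parent may still refuse all data use, and those outcomes would remain missing.

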10.2 Withdrawal of a Subject from the Study

A subject may withdraw consent (through their legally authorized representative) at any time without prejudice to further care.

If a subject is discharged or transferred to another hospital before 36 weeks PMA, the clinical status, including presence or absence of BPD at 36 weeks PMA, should be obtained. If, for any reason, the status of a subject is unknown (eg, subject is discharged home), every effort must be made to contact the subject's legally authorized representative to determine the status of the subject, including phone calls and certified letter(s). If the status of the subject has not been established in 28 days after the subject reaches 36 weeks PMA, the subject will be considered lost to follow-up. Note: All attempts should be made to ensure that no subjects are lost to follow-up.

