3.3.1 Duration of Subject Study Participation

The total duration of study participation for each subject in the primary phase of the study will be from enrollment (\leq 6 hours from birth) to 36 weeks PMA (or 28 days of life, whichever occurs last). Each subject will participate in a follow-up phase through 12 months corrected age (12 months after the subject's anticipated full-term due date [40 weeks PMA]). Subjects who complete all assessments and procedures up to and including the Final Visit (to occur at 36 weeks PMA, hospital discharge, or hospital transfer, whichever occurs first) will be considered study completers. Details regarding subjects who withdraw from the study before completion are provided in Section 10.

Study participation will consist of the following study phases and periods (assessments, procedures, and visits occurring in each of these phases can be found in Section 1.2):

Primary Phase:

- Screening Period: To occur in a timely manner to allow for study randomization \leq 6 hours from birth.
 - Study consent must be completed before any study-specific screening procedures that would not otherwise be performed in accordance with standard of care and local institutional practices.
- Primary Period: Time of start of initial treatment (T_0 on study) to 72 hours of life.
- Extended Period: $>$ 72 hours of life to Study Day 7.
- Final Period: Study Day 8 to Final Visit at 36 weeks PMA (\pm 2 days), death, hospital discharge, or hospital transfer (whichever occurs first); however, subjects must remain in the study until 28 days of life (ie, 36 weeks PMA \pm 2 days or 28 days of life, whichever occurs last).

Longer-Term Follow-Up Phase:

- Longer-Term Follow-Up Period: Evaluations occur at 6- and 12-months corrected age.

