8.1.2 Gas Exchange Parameters

Oxygen (O_2) saturation for each subject will be monitored by pulse oximetry (SpO_2); PCO_2 will be assessed for each subject by a transcutaneous monitor (eg, SenTec). Values for gas exchange parameters (PCO_2 , FiO_2 , SpO_2) and PEEP will be documented at randomization (\pm 5 minutes) and every 30 minutes following randomization until study treatment initiation (active or sham). The transcutaneous monitor must be calibrated for accuracy against a blood gas value (arterial, capillary, or venous) at the time of initial set-up and recalibrated, as necessary, in accordance with local institutional practices to ensure accuracy of the monitor output.

Gas exchange parameters will be recorded:

- Study Days 1-3: time 0 (T_0 ; study treatment initiation), 10, 20, 30, 40, 50, 60, 70, 80, 90, 100, 110, 120, 130, 140, 150 minutes (± 3 minutes) after initiation; 3 ± 0.5 , 6 ± 1 , 9 ± 1 , 12 ± 1 , 18 ± 2 , 24 ± 2 , 36 ± 2 , 48 ± 2 , 60 ± 2 and 72 ± 2 hours after initiation.
- Repeat study treatments: treatment initiation, 10, 20, 30, 40, 50, 60, 70 minutes (± 3 minutes) after initiation.
- Study Days 4-7 for FiO_2 and SpO_2 : daily at 0800 and 2000 hours (± 2 hours).
- Final Visit: FiO_2

If timing for measurements overlap, only one measurement should be taken.

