8.7.5.2 Documentation during Final Period

From Study Day 8 until the subject completes the study (36 weeks PMA [or 28 days of life, whichever is later], discharged, transferred, or dies, whichever occurs first), the date and time of each intubation and change of respiratory support must be documented in the study eCRF. If the subject is discharged or transferred to another hospital prior to 36 weeks PMA, the time of discharge or transfer will be documented in the study eCRF. If the subject is on respiratory support at the time of discharge or transfer, the type of respiratory support and the mode must be documented in the study eCRF.

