4.2.3 Other Secondary Endpoints

For other secondary endpoints include common complications of prematurity, gas exchange parameters (ie, FiO_2 , transcutaneous PCO_2 , SpO_2), duration of MV and oxygen requirement (the sum of all time periods using MV and supplemental oxygen through 36 weeks PMA, respectively), and duration and number of re-hospitalization and urgent care visits (through 12 months corrected age) will be summarized by treatment group. The reason for re-hospitalization and urgent care visits and respiratory medications (through 12 months corrected age) will be listed.

Common complications of prematurity through 36 weeks PMA (apnea, air leak, IVH, PVL, pulmonary hemorrhage, NEC, PDA, acquired sepsis, and ROP) will be summarized by treatment group using frequency and percent by treatment group.

Change in FiO_2 is defined as the change from baseline (initiation of treatment for active subjects or completion of patient interface setup for control subjects) through 72 hours post-randomization, and over the first 7 days of life. Change in transcutaneous PCO_2 is defined as the change from baseline (initiation of treatment for active subjects or completion of patient interface setup for control subjects) through 72 hours post-randomization. Change in transcutaneous SpO_2 is defined as the change from baseline (initiation of treatment for active subjects or completion of patient interface setup for control subjects) through 72 hours post-randomization.

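### An infant who leaves hospital still on support has no required MV or oxygen stop date and no stated rule for scoring the duration; the BPD severity grade is left open for some of these infants

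*Protocol*

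**What the plan says.** **Recording.** From Study Day 8, Protocol 8.7.5.2 requires support changes to be dated until the infant reaches the end of the primary phase or is "discharged, transferred, or dies, whichever occurs first), the date and time of each intubation and change of respiratory support must be documented". For an infant leaving on support it adds: "If the subject is on respiratory support at the time of discharge or transfer, the type of respiratory support and the mode must be documented". FiO2 is also taken at that point, since Protocol 8.1.2 lists "Final Visit: FiO_2" and the Final Visit can be the day of discharge or transfer (Appendix 1).

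**Status of leavers.** Protocol 3.3.1 treats infants who finish all assessments up to a Final Visit at 36 weeks, "hospital discharge, or hospital transfer, whichever occurs first) will be considered study completers".

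**Retrieval.** For discharge or transfer before 36 weeks PMA, Protocol 10.2 states that "the clinical status, including presence or absence of BPD at 36 weeks PMA, should be obtained", and requires every effort to reach the family if status is unknown.

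**Scoring.** SAP 4.2.3 defines the two durations as "the sum of all time periods using MV and supplemental oxygen through 36 weeks PMA, respectively". SAP 4.3 rules out imputation: "only available data will be considered". SAP 4.2.2 grades BPD severity in infants with at least 28 days of oxygen, by oxygen level or positive pressure at 36 weeks PMA or discharge.

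**The concern.** The endpoint runs to 36 weeks PMA, but the required record can end weeks earlier. A site can meet every requirement and never supply the date on which MV or oxygen stopped. Because leavers count as completers, nothing in the plan marks the record as cut short.

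Duration of MV is part of the study objective (Protocol 4.1). With oxygen requirement it is an other secondary endpoint (4.3.3); BPD severity is a key secondary endpoint (4.3.2). The dosage rationale (3.2.3.5) already leans on numerically shorter MV and oxygen time in Study 03-CL-1202. SAP 4.2 says that the between-arm delta for primary and secondary endpoints may be used to plan further studies and to support efficacy. A duration shortened by transfer would look like a better outcome. If leaving on support differed between arms, the delta would be distorted. If it did not, both means would still be too low.

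**Working it through.** The plan states no figure to reproduce. The check traces the rules and then does the day arithmetic.

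**Step 1: is the interval from leaving to 36 weeks collected anywhere?**
- Protocol 8.7.5.2: no. Dating stops at discharge or transfer; only type and mode on leaving are kept.
- Protocol 10.2: not by name. Status at 36 weeks does not reveal how many days of MV or oxygen came before it.
- Schedule of Activities, post-36-weeks column: it appears to serve infants discharged after 36 weeks.
- Protocol 8.7.5.3: total time per ventilatory mode is asked at 6 and 12 months, under the longer-term follow-up phase and with no stated start point. It does not clearly cover this interval, and the SAP Executive Summary cancels follow-up.

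**Step 2: how is a cut-off duration scored?** SAP 4.2.3 sums periods and 4.3 uses what is available. No sentence covers an infant who leaves on support. Summing the recorded periods is the most natural reading.

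**Step 3: size for one infant.** Inputs: gestational age 26 0/7 to 32 6/7 (Protocol 5.2). Days of leaving are assumed. Support is assumed continuous from birth to 36 weeks.

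Days from birth to 36 weeks = 252 − gestational age in days. Unrecorded days = that figure − day of leaving, with a floor of 0.

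| Gestational age | Days to 36 weeks | Leaves day 14: unrecorded | Share recorded | Leaves day 28: unrecorded |
|---|---|---|---|---|
| 26 0/7 | 252 − 182 = 70 | 56 | 14/70 = 20% | 42 |
| 28 6/7 | 252 − 202 = 50 | 36 | 14/50 = 28% | 22 |
| 29 0/7 | 252 − 203 = 49 | 35 | 14/49 = 29% | 21 |
| 32 6/7 | 252 − 230 = 22 | 8 | 14/22 = 64% | 0 |

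**Step 4: size for an arm, by assumption only.** Understatement of the arm mean = proportion leaving on support × mean days of support remaining. With 5% and 7 days: 0.05 × 7 = 0.35 days. With 20% and 21 days: 0.20 × 21 = 4.2 days. A 5-point difference between arms with 14 days remaining gives 0.05 × 14 = 0.7 days. The documents give neither a transfer rate nor days remaining. The upper figure cannot apply to the oldest infants: at 32 6/7, 21 days remaining would mean leaving on day 1 (22 − 21).

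**Step 5: BPD severity.** Final Visit FiO2 and the type and mode on leaving supply the inputs for a grade at discharge. Three gaps remain:
- An infant who leaves on oxygen before day 28 cannot have the 28-day condition confirmed from the required primary-phase records.
- SAP 4.2.2 mentions discharge but not transfer.
- A discharge-day grade refers to a different date from BPD yes/no at 36 weeks.

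**The case against.** **Retrieval is wider than BPD.** A reader might infer that 10.2 collects BPD yes/no and nothing else. The text does not support that: it asks for clinical status and gives BPD as an included item. This stands. But status at one date is not a history of start and stop dates, so the duration gap remains.

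**Severity.** A reader might infer that infants who leave early have no severity grade. SAP 4.2.2 contradicts that by allowing a grade at discharge, and the data for it are collected. Only the three gaps in Step 5 survive.

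**Scoring is not stated.** No text says that a cut-off duration is entered as complete; it could be set to missing. This also stands. The shortened value is an inference, and the defect is the missing rule.

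**Follow-up might have filled the interval.** Protocol 8.7.5.3 gives no start point, whereas 8.10.3 explicitly starts at 36 weeks PMA, so the total could have reached back. It is unclear that it would, and the SAP has cancelled follow-up.

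**Little hangs on it here.** Twelve infants were enrolled and no testing is planned. SAP section 11 lists no table for duration or BPD severity. The respiratory support listing (5.2) shows data by subject. All of this is true and limits the present effect, although SAP 4.2.2 and 4.2.3 still commit to summarising both by treatment group.

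**Conclusion.** The point holds for MV and oxygen duration. Recording ends on leaving, the required contact does not name stop dates, leavers count as completers, and the SAP sums periods without a rule for records that are cut off. Following the plan as written would most naturally understate duration for any infant who leaves on support. For an infant who leaves on day 14 and stays on support to 36 weeks, the recorded share ranges from 20% of the true time at 26 0/7 to 64% at 32 6/7.

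For BPD severity the point is narrow: the 28-day condition in early leavers, the unstated status of transfer, and the date mismatch.

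A bias between arms should not be inferred from the documents. They give no transfer rate, no timing and no sign of a difference by arm; 0.35 to 4.2 days and 0.7 days only illustrate stated assumptions. The effect in the 12 enrolled infants is small. The point matters mainly if the delta is carried into planning or the protocol is reused.

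**What to change.** - **Protocol 10.2:** add to the status contact already required the start and stop dates of MV and of supplemental oxygen through 36 weeks PMA (which also settles the 28-day count), and FiO2 and positive pressure at 36 weeks PMA.
- **SAP 4.2.3:** do not count a duration cut off by discharge or transfer on support as complete. Flag it as incomplete and show the number by arm.
- **SAP 4.2.2:** state whether discharge includes transfer.

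A Kaplan-Meier or restricted-mean summary censored at leaving is not proposed. The endpoint adds up possibly separate periods, so censoring accumulated time at transfer is likely to be informative, and deaths before 36 weeks would need their own rule.

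The cost is a few more items in an existing contact and two SAP sentences. For this study the protocol change would probably recover nothing: the last visit was expected on 19 January 2021 and the SAP is dated 1 August 2021. The SAP flag and the by-subject respiratory support listing are what remain practicable for the 12 infants.
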